5.2 Handling of Missing Data

Missing data will not be imputed.

6. Statistical Methods

6.1 General Principles

All data processing, summarization and analyses will be performed using Covance's SAS® Environment /Version 9.4 (or later) of the SAS® statistical software package.

The following principles will be applied to all TFLs unless otherwise stated:

Principle	Value
	Cohort 1A
Cohort labels and order	Cohort 1B
presented	Cohort 2
	Data in summary tables presented by cohort and
Tables	overall, and visit (where applicable).
	All data collected presented by cohort, subject,
	and visit (where applicable), unless otherwise
Listings	specified.
Descriptive summary statistics	Number of subjects (N), mean, standard deviation
for continuous variables	(SD), median, minimum, and maximum.
Descriptive summary statistics	
for categorical variables	Frequency counts and percentages [n (%)]
	Number of subjects at each cohort unless stated
Denominator for percentages	otherwise in table shell(s)
	Yes, included for demographics and other baseline
	characteristics when the number of missing is
	greater than zero for at least one cohort and one
Tools do NMississell as astorous	age group. Missing post-baseline values will not be
Include "Missing" as category	summarized, unless otherwise specified.
Display for percentages	One decimal place, except for 100%
Display for 0 percentages	0
Display to one more decimal	
place than collected value	Mean, Median, Percentiles
Display to two more decimal	
places than collected value	Standard Deviation
Date Format	DDMMMYYYY

6.2 Subject Disposition

Subject disposition will be listed and summarized by cohort, and overall, and will include:

- Number of subjects enrolled
- Number of subjects in FAS
- Number and percentage of subjects who complete the study

Sponsor Name: Sarepta Therapeutics, Inc.

Sponsor Protocol ID: 9004-101 Covance Study ID: 000000209191

• Number and percentage of subjects who discontinue the study, including a breakdown of the reasons for premature study discontinuation

6.3 Protocol Deviations

Not applicable.

6.4 Demographics and Other Baseline Characteristics

Demographic data recorded in eCRF will be listed and summarized by cohort and overall for the FAS. Standard descriptive statistics will be presented for the continuous variables of:

- Age at enrollment (years), calculated as (date of informed consent date of birth + 1)/365.25 rounded down to the nearest integer
- Age of disease onset (years)

The number and percentage of subjects will be presented for the categorical variables of:

- gender (Female, Male)
- race (American Indian or Alaska Native, Asian, Black or African American, Native Hawaiian or Other Pacific Islander, White, Unknown or Not Reported)
- ethnicity (Hispanic or Latino, Not Hispanic or Latino, Unknown or Not Reported)

6.4.1 Medical History

Medical history data recorded in eCRF will be listed. The number and percentage of subjects with any medical history will be summarized by medical history term by cohort and overall, for the FAS. Table will be sorted in descending overall frequency by medical history term.

6.4.2 Prior and Concomitant Medications/Therapies

Prior and concomitant medications/therapies will be listed. Prior medications or therapies are defined as medications or therapies with a start date and a stop date prior to Day 1. Concomitant medications or therapies are defined as medications or therapies with a start date on or after Day 1, or those with a start date before Day 1 and a stop date on or after Day 1 or ongoing. If a medication or therapy cannot be classified as one of the above categories due to incomplete start/end dates, it will be classified as concomitant.

Prior medications and concomitant medications will be listed together and summarized, separately, by cohort and overall, for the FAS. The number and percentage of subjects using each medication/therapy will be summarized. Tables will be sorted in descending overall frequency by medication/therapy.

Sponsor Name: Sarepta Therapeutics, Inc.

Sponsor Protocol ID: 9004-101 Covance Study ID: 000000209191

6.5 Efficacy Analyses

All efficacy analyses will be performed using FAS. All efficacy data recorded in eCRF will be listed.

6.5.1 Primary Efficacy Analysis

Not applicable.

6.5.2 Secondary Efficacy Analysis

The secondary efficacy measure is total distance covered in the 6MWT (meters) as recorded in the eCRF. Standard descriptive statistics will be used to summarize observed values, changes from baseline, and percent changes from baseline (i.e., changes from baseline divided by baseline values) at each visit (on days 60, 90, 180, and at months 9, 12, 18, and 24) by cohort and overall.

6.6 Safety Analyses

All safety analyses will be performed using FAS.

6.6.1 Extent of Exposure

All exposure data recorded in eCRF will be listed.

6.6.2 Adverse Events

Adverse events (AEs) will be coded using the Medical Dictionary for Regulatory Activities (MedDRA) [Version 22.0].

AEs will be graded by the Investigator as follows:

- Grade 1: Mild; asymptomatic or mild symptoms; clinical or diagnostic observations only; intervention not indicated
- Grade 2: Moderate; minimal, local or noninvasive intervention indicated; limiting age-appropriate instrumental activities of daily living (ADL)*
- Grade 3: Severe or medically significant but not immediately life-threatening; hospitalization or prolongation of hospitalization indicated; disabling; limiting self-care ADL**
- Grade 4: Life-threatening consequences; urgent intervention indicated

Sponsor Protocol ID: 9004-101 Covance Study ID: 000000209191

Grade 5: Death related to AE

A Semi-colon indicates 'or' within the description of the grade.

- *Instrumental ADL refer to preparing meals, shopping for groceries or clothes, using the telephone, managing money, etc.
- **Self-care ADL refer to bathing, dressing and undressing, feeding self, using the toilet, taking medications, and not bedridden.

The relationship between an AE and study drug is assessed as definite, probable, possible, unlikely, or not related. A treatment-related AE is an AE considered by the investigator as definitely, possibly, or probably related to study drug or with unknown/missing relationship to study drug.

All AE data recorded in eCRF will be listed. In addition, a listing of serious AEs (SAEs) will be produced.

Treatment-emergent AEs (TEAEs) will be summarized by cohort and overall. TEAEs are AEs that occur or worsen in severity on or after gene transfer. AEs with missing start date will be considered as TEAEs.

TEAEs will be summarized by cohort and overall. An overview table will summarize the number and percentage of subjects with at least one of the following TEAEs, where subjects with more than one TEAE in a particular category are counted only once in that category:

- Any TEAE
- TEAE by maximum severity grade
- Treatment-related TEAE
- Any treatment-emergent SAE (TESAE)
- Treatment-related TESAE
- TESAE leading to death

The number of total TEAEs will be also included in the overview table.

The number and percentage of subjects reporting each AE will be summarized by System Organ Class (SOC) and Preferred Term (PT), or PT. Tables will be sorted in descending overall frequency by SOC, and then in descending overall frequency by PT within SOC, and then alphabetically. The table summarized by PT will be sorted in descending overall frequency by PT and then alphabetically. The following summaries will be produced:

- TEAEs, by SOC and PT
- TEAEs, by PT
- TEAEs, by SOC, PT, and maximum severity grade
- Treatment-related TEAEs, by SOC and PT
- TESAEs, by SOC and PT
- Treatment-related TESAEs, by SOC and PT
- TESAEs leading to death, by SOC and PT

In the above summaries, subjects with more than one AE within a particular SOC will be counted only once for that SOC. Similarly, subjects with more than one AE within a particular PT will be counted only once for that PT. For summaries by maximum

Sponsor Name: Sarepta Therapeutics, Inc.

Sponsor Protocol ID: 9004-101 Covance Study ID: 000000209191

severity grade, subjects with multiple AEs within a particular SOC or PT will be counted under the category of their most severe grade within that SOC or PT.

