4.0 SPECIFIC AIMS

4.1 PRIMARY OBJECTIVE

Determine the safety of intravascular administration of self-complementary scAAVrh74.tMCK.hSGCA delivered via a major lower limb artery targeting all of the lower limb muscles of LGMD2D (alpha-SG deficient) subjects.

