8.0 ADVERSE EVENT MONITORING AND REPORTING

8.1 DEFINITION OF AN ADVERSE EVENT

As stated above (6.2.7.4) this protocol will follow the final regulations issued by the Food and Drug Administration addressing the safety reporting requirements for investigational new drug applications (INDs) found in 21 CFR part 312 and for bioavailability and bioequivalence studies found in 21 CFR part 320. "Safety Reporting Requirements for INDs and BA/BE Studies".

<http://www.fda.gov/downloads/Drugs/GuidanceComplianceRegulatoryInformation/Guidances/UCM227351.pdf>

Adverse Events will be collected throughout the study from enrollment to last follow up visit.

Adverse Event (AE): Adverse event means any untoward medical occurrence associated with the use of a drug in humans, whether or not considered drug related.

Adverse events will be graded by the investigator accordingly:

Grade 1 Mild; asymptomatic or mild symptoms; clinical or diagnostic observations only; intervention not indicated.

Grade 2 Moderate; minimal, local or noninvasive intervention indicated; limiting age-appropriate instrumental ADL*.

Grade 3 Severe or medically significant but not immediately life-threatening; hospitalization or prolongation of hospitalization indicated; disabling; limiting self care ADL**.

Grade 4 Life-threatening consequences; urgent intervention indicated.

Grade 5 Death related to AE.

A Semi-colon indicates 'or' within the description of the grade.

A single dash (-) indicates a grade is not available.

Activities of Daily Living (ADL)

*Instrumental ADL refer to preparing meals, shopping for groceries or clothes, using the telephone, managing money, etc.

**Self care ADL refer to bathing, dressing and undressing, feeding self, using the toilet, taking medications, and not bedridden.

Association or relatedness to the study agent, study procedures and the subject's pre-existing disease will be graded as follows: 5 = unrelated, 4 = unlikely, 3 = possibly, 2 = probably, and 1 = definitely related.

Adverse reaction: An adverse reaction means any adverse event caused by a drug. Adverse reactions are a subset of all suspected adverse reactions for which there is reason to conclude that the drug caused the event.

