11.3.2.2 CANNULATION OF THE FEMORAL ARTERY AND FEMORAL VEIN

The risks of limb artery canulation include rarely permanent ischemic damage, sepsis, local infection, pseudoaneurysm, hematoma, and bleeding. Large artery canulation is used routinely

in the following clinical situations: extracorporeal membrane oxygenation (in >10 kg patients) and isolated limb perfusion for the treatment of limb soft tissue sarcomas. Small artery canulation is used in acute care settings for invasive blood pressure monitoring and blood sampling. At the puncture site: bruising at the site where the catheter is inserted is common (usually in the groin). Occasionally, a larger bruise/swelling (hematoma) which may require transfusion, surgery or delayed discharge may occur. The risk of this is less than 4% (or 1 in 25). The risk of the vessel becoming blocked or being significantly damaged at the insertion site is less than 0.5% (or 1 in 200). To minimize risk to the limb and subject we are targeting the femoral vessels in the current protocol. In addition the subject will be heparinized (monitored by Activated Clotting Time measurements) to minimize the risk of thrombosis/emboli. In ILP/ILI procedures there is a small risk of compartment syndrome. This outcome is minimized in our protocol by utilizing pressure servo-regulating pump flows.

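### Adverse events attributed to the delivery procedure but judged unlikely or not related to study drug enter no related-event table in the SAP, and no procedure-related summary is planned

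*SAP*

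**What the plan says.** SAP 6.6.2 describes one causality assessment: "The relationship between an AE and study drug is assessed as definite, probable, possible, unlikely, or not related". It then defines the reporting category: "A treatment-related AE is an AE considered by the investigator as definitely, possibly, or probably related to study drug", extended in the same sentence to events "or with unknown/missing relationship to study drug".

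That category feeds three sets of output:
- two rows of the overview table in SAP 6.6.2 (related TEAEs and related TESAEs);
- two SOC/PT tables, of which one is "Treatment-related TEAEs, by SOC and PT" and the other is its TESAE counterpart;
- the treatment-related version of the risk tables in SAP 6.6.2.1, run for both the important potential risks and the other risks.

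Protocol 8.1 asks for more: "Association or relatedness to the study agent, study procedures and the subject's pre-existing disease will be graded as follows", followed by a five-point scale.

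The primary objective in Protocol 4.1, repeated in SAP 2.1.1, is: "Determine the safety of intravascular administration of self-complementary scAAVrh74.tMCK.hSGCA delivered via a major lower limb artery". Protocol 11.3.2.2 to 11.3.2.8 describe harms of the delivery itself. They include a larger hematoma "which may require transfusion, surgery or delayed discharge may occur", vessel blockage, compartment syndrome, lymphedema, neuropathy, and ischemic and reperfusion injury.

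**The concern.** In this trial the vector and its route of delivery are tested together, and the objective is worded around the administration. Harm from arterial and venous access, balloon occlusion or infusion is therefore harm from the intervention. With seven subjects and no control arm, investigator attribution is the main way the tables can separate such harm from the disease background.

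The protocol has the investigator judge procedure relatedness, but the analysis plan never uses that judgement. An access-site hematoma could reasonably be graded as related to the procedure and unrelated to the vector. It would then be missing from the tables a reader consults to see what the treatment caused. The named risk categories in SAP 6.6.2.1.1 and 6.6.2.1.2 do not fill the gap. They cover hepatotoxicity, hypersensitivity, thrombocytopenia, shedding, rhabdomyolysis and viral integration, and none is aimed at vascular access or limb isolation.

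**Working it through.** The plan gives no figure on this point to reproduce. The check applies the SAP rule to each possible grading and then gives a sense of scale.

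**Step 1: which gradings are left out.** Take an event with a positive procedure grade (possible, probable or definite: 3 levels). Cross it with the drug relationship (the five SAP categories plus unknown/missing: 6 levels). That gives 3 × 6 = 18 combinations.

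| Drug relationship | Counted as treatment-related? | Combinations |
|---|---|---|
| Definite, probable, possible | Yes | 3 × 3 = 9 |
| Unknown/missing | Yes | 1 × 3 = 3 |
| Unlikely, not related | No | 2 × 3 = 6 |

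So 12 of 18 are included and 6 of 18 are left out. This counts combinations and is not an expected share of events. With a combined drug-and/or-procedure definition, 0 of 18 would be left out.

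**Step 2: which outputs are affected.** Two of the six overview rows and two of the seven SOC/PT tables in SAP 6.6.2 use the related definition, as does one of the four table types in SAP 6.6.2.1. The others are not restricted by causality. All AE data and all SAEs are listed as well.

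**Step 3: scale.** Protocol 11.3.2.2 puts the risk of a larger hematoma below 4%, without saying whether this is per subject, limb or puncture. Enrolment is 1 single-limb and 6 bilateral subjects, so 7 subjects and 1 + 6 × 2 = 13 limbs. Assume independence and take a rate p. The chance of at least one event in n is 1 − (1 − p)^n.

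| p | 7 subjects | 13 limbs |
|---|---|---|
| 4% (upper bound used as the rate) | 1 − 0.96^7 = 24.9% | 1 − 0.96^13 = 41.2% |
| 2% | 1 − 0.98^7 = 13.2% | 1 − 0.98^13 = 23.1% |
| 1% | 1 − 0.99^7 = 6.8% | 1 − 0.99^13 = 12.2% |

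These are chances that a hematoma occurs, not that one is left out of the related tables.

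**Step 4: effect of one left-out subject.** Percentages use the number of subjects in the cohort (SAP 6.1), and the overview counts each subject once per category. One subject is 1/3 = 33 percentage points in Cohort 1B or 2, and 1/7 = 14 points overall. The overview rate moves by that much only if the subject has no other event already counted as related.

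**The case against.** The strongest case against is that nothing is lost. Any treatment-emergent event, whatever its cause, enters the all-TEAE tables and, if serious, the TESAE tables. Listings are by cohort and subject, so with seven subjects each event can be read individually. The SAP's safety endpoint is adverse events, not related adverse events, so neither document makes the related-event rate the test of the primary objective. The drug-based definition also matches Protocol 7.4 and 7.5, where dose-limiting toxicity and the enrolment halt are tied to the study agent or study drug. Protocol 12.1 separately brings severe local complications of administration under the halt rule, so they reach the DSMB whatever label the SAP gives them. Replacing the drug-only definition would blur vector toxicity with catheter complications.

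Most of this stands. It is why the drug-only tables should stay and why the point concerns labelling rather than lost data. It does not remove the gap: the all-causality tables do not say which events the intervention caused, and the plan has no summary that does so for delivery harms.

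It is also fair that the CRF is not among the documents. The SAP describes only a drug-relationship assessment, so a separately recorded procedure grade cannot be confirmed.

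**Conclusion.** The point holds in a limited form. Events attributed to study procedures and judged unlikely or not related to study drug enter no related-event table, and no planned output uses the procedure grade that Protocol 8.1 calls for. For a trial whose primary objective is the safety of the administration, that is a real but inexpensive gap to close.

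Three stronger readings are tempting, and the documents do not support them.
- A reader might infer that an event counts only if judged related to study drug. The SAP also counts unknown or missing relationships.
- A reader might infer that all procedure-related harms are missing from the related tables. Protocol 8.1 does not make the attributions mutually exclusive, so an event graded related to both drug and procedure is already included.
- A reader might take 25% or 41% as the chance that a harm goes unreported. Those figures use an upper bound as the rate, assume independence and an unstated unit, and concern occurrence only.

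One limit on the all-causality tables as a safety net: the SAP defines TEAEs from gene transfer onward. It does not say whether an event during cannulation, shortly before infusion on the same day, qualifies.

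**What to change.** In SAP 6.6.2, keep the drug-related tables as they are and add:
- overview rows and SOC/PT tables for procedure-related TEAEs and TESAEs, counting possible, probable and definite grades;
- the same rows and tables for TEAEs and TESAEs related to study drug and/or study procedure.

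Use the procedure grade required by Protocol 8.1, and report the combined summary beside the drug-only one against the primary objective. If the eCRF did not capture the procedure grade separately, the SAP should say so, so that readers know why delivery harms cannot be summarised by attribution.

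The cost is some SAP wording and a few extra runs of existing table programs. No new data are needed if the grade was captured. The combined related-event rate may look less favourable than the drug-only one.

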6.6.2.1 TEAEs Meeting the Criteria of Each Risk

The following tables will be created:

- Summary of TEAE meeting the criteria of important risk by SOC, PT by important risk
- Summary of treatment-related TEAEs meeting the criteria of important risk by SOC, PT by important risk
- Summary of TEAEs meeting the criteria of important risk by SOC, PT, and maximum severity by important risk
- Summary of TESAEs meeting the criteria of important risk by SOC, PT by important risk

All standardized MedDRA Queries (SMQs) based on MedDRA [Version 22.0] listed below will include broad and narrow terms.

6.6.2.1.1 Important Potential Risks

- Hepatotoxicity: SMQ Hepatic failure, Fibrosis and cirrhosis and other liver damage-related conditions; SMQ Hepatitis, non-infectious; SMQ Cholestasis and jaundice of hepatic origin; SMQ Liver-related investigations, signs and symptoms; SMQ Liver-related coagulation and bleeding disturbances
- Hypersensitivity including autoimmune inflammation: SMQ
 Hypersensitivity; PT Autoimmune myositis; PT Autoimmune myocarditis; PT
 Autoimmune hepatitis; PT Haemolytic uraemic syndrome; PT Atypical
 haemolytic uraemic syndrome; PT Thrombotic microangiopathy; PT Acute
 kidney injury; PT Microangiopathic haemolytic anaemia; PT Red cell
 fragmentation syndrome and HLT Immune response protein analyses NEC
- Thrombocytopenia: SMO Hematopoietic thrombocytopenia

6.6.2.1.2 Other Risks

The summarization tables in section 6.6.2.1 will also be provided for other risks including:

- Vector shedding and transmission: PT Viraemia; PT Transmission of an infectious agent via product and HLT Pathways and sources of exposure
- **Rhabdomyolysis:** SMQ Rhabdomyolysis/myopathy
- Viral integration: SMQ Malignancies

In the above summaries, subjects with more than one AE within a particular risk category will be counted only once for that risk category. Subjects with more than one AE within a particular SOC will be counted only once for that SOC. Similarly, subjects with more than one AE within a particular PT will be counted only once for that PT. For summaries by maximum severity grade, subjects with multiple AEs

Sponsor Protocol ID: 9004-101 Covance Study ID: 000000209191

within a particular risk, SOC or PT will be counted under the category of their most severe grade within that risk, SOC or PT.

6.6.3 Laboratory Evaluations

All laboratory data recorded in eCRF will be listed.

The observed laboratory data, change from baseline, and percent changes from baseline for the following hematology and general chemistry laboratory tests will be summarized using standard descriptive statistics by cohort and overall, and by visit. For urinalysis laboratory tests listed below, the number and percentage of subjects with each assessment category will be presented.

Laboratory Category	Laboratory Test
Hematology	White blood cell (WBC), Hemoglobin, Hematocrit, Platelet count, Mean corpuscular volume (MCV), Mean corpuscular hemoglobin (MCH), Mean corpuscular hemoglobin concentration (MCHC), Red cell distribution width (RDW), Red blood cell (RBC), Neutrophil, Segmented neutrophil, Lymphocyte, Monocyte, Eosinophils, Basophils, Bands, Mean platelet volume (MPV)
Chemistry	Sodium, Potassium, Chloride, Carbon dioxide, Blood urea nitrogen (BUN), Creatinine, Glucose, Total protein, Total bilrubin, Alanine aminotransferase (ALT), Aspartate aminotransferase (AST), Alkaline phosphatase (ALP), Gamma glutamyl transferase (GGT), Amylase, Creatine kinase (CK), Cystatin C, Prothrombin time (PT), International normalized ratio (INR), Activated partial thromboplastin time (aPTT), Fibrinogen
Urinalysis	Color, Appearance, Specific gravity, pH, Protein, Glucose, Ketones, Bilirubin, Occult Blood, Nitrite, Urobilinogen, Leukocyte Esterase, Microscopic Urine, RBC, WBC, Mucus, Epithelial Cells Specimen Microscopic Examination

Line plots of liver function tests including ALT, AST, total bilurubin, GGT, total protein, ALP, platelets, INR, and PT over time will be created by subject.

The eDISH (evaluation of Drug-Induced Serious Hepatotoxicity) plots will be provided, ALT (x baseline) and GGT (x upper limit of normal [ULN]) will be plotted against total Bilirubin (x ULN) based on maximum elevation any time post baseline.

